8.3. Subgroup Analyses

To assess the homogeneity of treatment effects among subgroups, descriptive summaries by age groups (< 65 vs \geq 65 years), sex (males or females), race (White vs Non-white), primary ocular diagnosis (POAG or OHT), and mean diurnal IOP at baseline (< 25 or \geq 25 mmHg) will be reported for primary efficacy endpoint.

Other subgroup analyses may be performed as suggested by the data.

9. SAFETY ANALYSES

Safety of DE-117 will be primarily assessed by AEs, BCVA and evaluation with slit-lamp biomicroscopy and ophthalmoscopy. The Safety population will be used for all safety summaries, where subjects will be classified by actual treatment received.

All the safety-related measures will be summarized descriptively by actual treatment received. Except AEs, the descriptive summary of each safety-related measure and the change from baseline in that measure will be performed if applicable.

9.1. Adverse Event

Subjects with any AE(s), SAE(s), SAR(s) serious SAR(s) and significant AE (AE leading to study drug discontinuation) will be tabulated by type of AE(s) for each actual treatment received.

Besides the overall AE summary, subjects with any AE(s) and any SAR(s) will be tabulated by SOC and preferred term. A subject who experienced multiple AEs within a SOC or preferred term will be counted only once for that SOC or preferred term.

The same analysis above will be performed for ocular AEs and non-ocular AEs.

AEs, AEs leading to death, AEs leading to study drug discontinuation, SAEs, SARs and ESIs, if any, will be listed separately.

9.2. Slit-lamp Biomicroscopy

For each biomicroscopy parameter, frequency and percentage of rating scores will be summarized by analysis visit for study eyes and non-study eyes, separately. In addition, any clinically significant worsening (increase) from baseline will be summarized and listed.

9.3. Ophthalmoscopy

Frequency and percentage of rating scores will be summarized by treatment and analysis visit for study eyes and non-study eyes, separately. In addition, any worsening (increase) of \geq 2 units from baseline will be summarized and listed.

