
 Any abnormal laboratory test results (hematology, clinical chemistry, or urinalysis) or other safety assessments (e.g., ECG, radiological scans, vital signs measurements), including those that worsen from baseline, considered clinically significant in the medical and scientific judgment of the investigator (and not related to progression of underlying disease [glaucoma or ocular hypertension], unless judged by the investigator to be more severe than expected for the subject's condition). Exacerbation of a chronic or intermittent pre-existing condition including either an increase in frequency and/or intensity of the condition. New conditions detected or diagnosed after study intervention administration even though it may have been present before the start of the study. Signs, symptoms, or the clinical sequelae of a suspected drug-drug interaction. Signs, symptoms, or the clinical sequelae of a suspected overdose of either study intervention or a concomitant medication. Overdose per se will not be reported as an AE/SAE unless it is an intentional overdose taken with possible suicidal/self-harming intent. Such overdoses should be reported regardless of sequelae. “Lack of efficacy” or “failure of expected pharmacological action” per se will not be reported as an AE or SAE. Such instances will be captured in the efficacy assessments. However, the signs, symptoms, and/or clinical sequelae resulting from lack of efficacy will be reported as AE or SAE if they fulfill the definition of an AE or SAE.
Events NOT Meeting the AE Definition

 Any clinically significant abnormal laboratory findings or other abnormal safety assessments which are associated with the underlying disease, unless judged by the investigator to be more severe than expected for the subject's condition. The disease/disorder being studied or expected progression, signs, or symptoms of the disease/disorder being studied, unless more severe than expected for the subject's condition. Medical or surgical procedure (e.g., endoscopy, appendectomy): the condition that leads to the procedure is the AE. Situations in which an untoward medical occurrence did not occur (social and/or convenience admission to a hospital). Anticipated day-to-day fluctuations of pre-existing disease(s) or condition(s) present or detected at the start of the study that do not worsen.

Table 8: Definition of SAE

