4.3.2. Safety Measures

Table 5 lists the safety measures to be evaluated for this study.

Table 5: Safety Assessments

| Safety Measures | Note |
|--|--|
| Slit-lamp biomicroscopy: anterior chamber cells anterior chamber flare lid hyperemia lid edema conjunctival (palpebral and bulbar) hyperemia conjunctival chemosis corneal edema corneal staining (with fluorescein) keratic precipitate anterior synechiae of iris posterior synechiae of iris | Anterior Chamber Cells will be graded as 0 = No cells, 0.5 = 1-5 cells, 1 = 6-15 cells, 2 = 16-25 cells, 3 = 26-50 cells, or 4 = > 50 cells. Anterior Chamber Flare will be graded as 0 = None, 1 = Faint, 2 = Moderate, 3 = Marked, or 4 = Intense. The other biomicroscopy parameters will be graded as 0 = None, 1 = Mild, 2 = Moderate, or 3 = Severe. |
| Ophthalmoscopy glaucomatous optic nerve cup to disc ratio retina macula choroid vitreous | Damage to optic nerve will be graded as 0 = None 1 = Mild, 2 = Moderate, 3 = Severe. Cup/disc ratio will be recorded with two decimal points (e.g., 0.80). Retina, macula, choroid, and vitreous will graded as 0 = Normal, 1 = Abnormal. |
| Best Corrected visual acuity | Best corrected visual acuity score measures the acuteness or clearness of corrected vision, with a range of [-0.30, 1.10] in logarithm of the minimum angle of resolution (logMAR) scale. A decrease in logMAR score indicates improvements in corrected visual acuity. |

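### The SAP's only ophthalmoscopy worsening rule, a rise of at least 2 units, cannot be met by the four fundus items scored 0 or 1

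*SAP*

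**What the plan says.** SAP 9.3 plans two outputs for ophthalmoscopy. The first is a table of counts and percentages of scores by treatment and visit, with study and non-study eyes kept apart. The second is a worsening output: an increase of at least "2 units from baseline will be summarized and listed". The section does not name the parameters the rule covers and does not define a unit.

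SAP Table 5 (Section 4.3.2) lists six ophthalmoscopy parameters on three kinds of scale:

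- Optic nerve: "Damage to optic nerve will be graded as 0 = None 1 = Mild, 2 = Moderate, 3 = Severe".
- Four structures: "Retina, macula, choroid, and vitreous will graded as 0 = Normal, 1 = Abnormal".
- Cup/disc ratio: a number recorded to two decimals.

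Protocol 8.2.2.9 gives the same 0 to 3 scale for the optic nerve. For the four structures it asks only about abnormality, with no finer grading.

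The neighbouring SAP sections use rules that fit their measures. SAP 9.2 (slit lamp) relies on clinically significant worsening with no fixed step, and SAP 9.4 (acuity) states its step as 0.2 logMAR, or two lines.

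**The concern.** A threshold of 2 cannot be reached on a scale that runs from 0 to 1. Ophthalmoscopy is a named safety endpoint in both documents, and the safety objective compares twice-daily with once-daily dosing. Protocol 8.2.2.10 says that macular edema has occurred in earlier trials of this drug, so the macula and retina are places a safety reader will look. A worsening listing with no macular or retinal entries could be read as evidence that the fundus did not worsen, when it is empty by construction.

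An examination-based listing also serves as a check on event reporting. For an abnormal assessment, the adverse event route depends on the investigator's judgement of clinical significance. A listing driven by the recorded grade does not.

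**Working it through.** **Inputs.** The threshold, an increase of at least 2, is from SAP 9.3. The scales are from SAP Table 5. The documents do not give the range of the cup/disc ratio, so 0 to 1 is assumed.

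**Can the rule be met?** For each scale, list every worsening step (post-baseline score above baseline score) and keep those where the difference is 2 or more.

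| Parameter | Scale | Largest increase | Worsening steps | Steps of 2 or more |
|---|---|---|---|---|
| Retina, macula, choroid, vitreous (each) | 0, 1 | 1 − 0 = 1 | 1 (0 to 1) | 0 |
| Optic nerve | 0, 1, 2, 3 | 3 − 0 = 3 | 6 | 3 (0 to 2, 0 to 3, 1 to 3) |
| Cup/disc ratio | assumed 0 to 1 | 1.00 | continuous | depends on the unit |

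So 4 of the 6 parameters cannot meet the rule. For cup/disc ratio, if a unit is 1.00 the required rise is 2.00, which exceeds the largest possible rise of 1.00. If a unit were 0.10 the required rise would be 2 × 0.10 = 0.20, which is reachable. The 0.10 reading is only an illustration; nothing in the documents sets it. For the four 0/1 items, no reading of *unit* as a grade step gives an increase of 2.

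**Could other planned outputs supply the same information?**

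1. *By-visit frequencies (SAP 9.3).* These give the abnormal count at each visit. New and resolved findings offset each other, so only the net change is visible.
2. *Change from baseline (SAP 9 and Protocol 9.3.7).* This is planned only where applicable, and SAP 9.3 does not name it for ophthalmoscopy as SAP 9.4 does for acuity. If the mean and SD were produced for a 0/1 item, the count could be recovered. As an illustration with assumed counts, take n = 50 eyes with 4 new and 3 resolved abnormalities:
   - Mean change = (4 − 3)/50 = 0.02.
   - SD = √[(7 − 50 × 0.02²)/49] = √(6.98/49) = 0.377.
   - Working back, new + resolved = 49 × SD² + 50 × mean² = 6.98 + 0.02 = 7, and new − resolved = 50 × 0.02 = 1. Hence new = (7 + 1)/2 = 4.
   - With the SD rounded to 0.38 the answer is 4.05, which still identifies 4.

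   So the count by arm could be recovered if that summary is produced, but the subjects would not be identified.
3. *Adverse events.* Protocol Table 7 (Section 10.2) counts abnormal safety assessments as adverse events, "including those that worsen from baseline, considered clinically significant in the medical and scientific judgment of the investigator". It also counts "New conditions detected or diagnosed after study intervention administration even though it may have been present before the start of the study". SAP 9.1 tabulates events by arm and adds: "The same analysis above will be performed for ocular AEs and non-ocular AEs". This route covers what the investigator reports.
4. *Events of special interest.* Macular edema is one, and under SAP 9.1 "SAEs, SARs and ESIs, if any, will be listed separately".

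That leaves one gap: a new abnormality on a 0/1 item that was not reported as an event has no committed examination-based count or subject-level listing.

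**The case against.** The strongest reply is that the 2-unit rule was meant only for the optic nerve grade, the one ordinal fundus scale in Table 5, with the normal/abnormal items left to the frequency table. On that reading the SAP lacks only a clarifying phrase. That is plausible, but SAP 9.3 does not say it. If it is right, the four items have no worsening rule at all, which leaves the same gap.

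The second reply is that other routes cover the clinical risk, and most of this stands. Adverse events are collected through the exit visit. Treatment-emergence extends to 2 days after the last dose (SAP 4.3.1), so for completers a finding at the Visit 4 examination falls inside the window. Ophthalmoscopy has only one scheduled post-baseline examination, so baseline and Week 6 abnormal counts will sit side by side. Analysis datasets are planned, so subject-level scores should remain available. What stays uncovered is largely findings the investigator judged not clinically significant. Misreading an empty listing would also require the reader to overlook the frequency and event tables. These points are why the matter is minor.

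Two further points stand. Comparing a dilated Week 6 examination with a Visit 2 examination for which no dilation is specified can produce apparent new findings that reflect better detection, so the remedy must deal with that. Restricting the rule to the optic nerve also leaves cup/disc ratio without a worsening threshold. That does not weaken the point about the four 0/1 items.

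**Conclusion.** The concern holds. As written, the rule cannot be met by 4 of the 6 ophthalmoscopy parameters: 0 of their 1 possible worsening step qualifies, against 3 of 6 for the optic nerve. This rests only on the scales in Table 5 and needs no assumption. The cup/disc result is undetermined, because it depends on an assumed 0 to 1 range and an undefined unit.

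The severity is minor. SAP 6 rules out statistical testing of safety measures, so no test result changes. The loss is a committed count and listing of new, unreported abnormalities in retina, macula, choroid and vitreous. The documents give no rate for such findings, so the number of subjects affected cannot be estimated.

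**What to change.** Amend SAP 9.3 as follows:

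1. State that the 2-unit rule applies to the optic nerve grade. Say also whether cup/disc ratio has a worsening threshold and, if so, define it in that ratio's own units.
2. For retina, macula, choroid and vitreous, summarise and list by arm any change from 0 at baseline (Visit 2) to 1, separately for study and fellow eyes.
3. In both the summary and the listing, show the Visit 1 result, for example by splitting each count into eyes normal at Visit 1 and eyes already abnormal at Visit 1. Dilation is specified at Visits 1 and 4 but not at Visit 2, so the split separates findings absent at both earlier examinations from those already seen under dilation at screening.

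The cost is a wording change plus one small table and listing. No new examination is needed: ophthalmoscopy is already scheduled at Visits 1, 2 and 4, and Protocol 10.1.9 has screening data entered in the eCRF. The drawback is slightly more output, with some incidental findings listed in both arms. A 0/1 grade still cannot show further worsening in an eye already abnormal at baseline; that remains with adverse event reporting.

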9.4. Best Corrected Visual Acuity

Corrected visual acuity scores measured in logMAR scale and changes from baseline will be summarized by actual treatment received and analysis visit for study eyes and fellow eyes, separately. In addition, any change such as worsening or improvement of at least 0.2 logMAR (2 lines) or maintained within 0.2 from baseline will be summarized. Subjects with worsening of at least 0.2 from baseline will be listed.

10. ANALYSES OF OTHER MEASURES

None.

11. REFERENCES

None.

12. APPENDICES

12.1. PROC MIXED for MMRM

```
PROC MIXED data = dataset_name METHOD=REML;
  WHERE fasfl='Y' AND paramcd=" IOP " AND avisitn IN (2, 6) AND steyefl='Y' AND atpt IN
  ('8:00', '12:00', '16:00');
  By atpt;
  CLASS usubjid trtpn avisitn;
  MODEL aval = base trtpn avisitn trtpn*avisitn/DDFM =KR;
  REPEATED avisitn/SUBJECT = usubjid TYPE= UN;
  LSMEANS trtpn*avisitn/DIFF CL;
  ESTIMATE "0.002% DE-117 QD - 0.002% DE-117 BID at Week 2" trtpn 1 -1
            trtpn*avisitn 1 0 -1 0 /CL;
  ESTIMATE " 0.002% DE-117 QD - 0.002% DE-117 BID at Week 6" trtpn 1 -1
            trtpn*avisitn 0 1 0 -1 /CL;
RUN;
```

where

- ✓ fasfl: Full Analysis Set Population Flag
- ✓ paramcd: Parameter Code
- ✓ avisitn: Analysis Visit (N)
- ✓ steyefl: Study Eye Flag
- ✓ usubjid: Unique Subject ID
- ✓ trtpn: Planned Treatment (N) for 0.002% DE-117 QD and 0.002% DE-117 BID
- ✓ aval: Post baseline IOP score
- ✓ base: Baseline Value

This is a representation of an electronic record that was signed electronically
and this page is the manifestation of the electronic signature.
